3.1.3 Overall visit response

Table 4 defines how the previously defined TL and NTL visit responses will be combined with new lesion information to give an overall visit response.

Table 4 Overall Visit Responses

Target Lesions	Non-target lesions	New Lesions	Overall Response
CR	CR or NA	No (or NE)	CR
NA	CR	No (or NE)	CR
CR	Non CR/Non PD (or NE)	No (or NE)	PR
PR	CR, Non CR/Non PD or NE, NA	No (or NE)	PR

Date 15 February 2022

Table 4 Overall Visit Responses

Target Lesions	Non-target lesions	New Lesions	Overall Response
GD.	CR, Non CR/Non PD or	N. (NE)	ap.
SD	NE, NA	No (or NE)	SD
NA	Non CR/Non PD	No (or NE)	SD
	CR, Non CR/Non PD or		
NE	NE, NA	No (or NE)	NE
NA	NE	No (or NE)	NE
DD	A	, ,	DD.
PD	Any	Any	PD
Any	PD	Any	PD
Any	Any	Yes	PD
NA	NA	No	NED
IVA	IVA	110	NLD

CR = complete response, PR = partial response, SD = stable disease, PD = progressive disease, NE = not evaluable, NED = no evidence of disease, NA = not applicable (only relevant if there were no TL/NTL at baseline).

3.1.4 Independent review

The independent review charter contains the details of the independent central review conducted by the AstraZeneca-appointed central Core Imaging Laboratory and will be developed in advance of the start of the study. The independent data review will provide RECIST measurements for each visit for each patient at the time of primary data cut-off (DCO). After the primary PFS analysis, central review of scans will no longer be required.

For each patient, the independent reviewer will provide time point response data and the relevant scan dates for each time point (i.e. for visits where progression is/is not identified) with supporting measurements and assessments.

3.2 Outcome Variables

At each visit patients will be assigned a RECIST visit response of CR, PR, SD, PD, NED (applies only to those patients entering the study with no evidence of disease at baseline), NE depending on the status of their disease compared to baseline and previous assessments, using programmatically derived overall visit response from Investigator RECIST assessments. This will be repeated using the time point responses and relevant dates from the BICR.

Where applicable, outcome variables will be programmatically derived using data from Investigator RECIST assessments unless otherwise stated.

Objective progression is defined as at least a 20% increase in the sum of the diameters of the target lesions (compared to previous minimum sum) and an absolute increase of > 5 mm, or an overall non-target lesion assessment of progression or a new lesion. For patients with no evidence of disease at baseline, following a complete radiological response to chemotherapy, progression is defined by the detection of new lesions on follow-up radiological assessments.

The primary analysis will be based on investigator-recorded assessment of the radiological scans.

A sensitivity analysis based on the BICR review of the radiological scans will be carried out.

The baseline RECIST assessment should be performed prior to randomisation but if an evaluable RECIST assessment occurs after randomisation but before treatment (and there is no available RECIST assessment before randomisation), then this assessment will be used as the baseline assessment. If a patient does not have a baseline RECIST scan performed prior to the date of first dose of study treatment (olaparib/placebo) then the patients will be censored at Day 1 in the analysis.

3.2.2 Time from randomisation to second progression or death (PFS2)

Time from randomisation to second progression or death is defined as the time from the date of randomisation to the earliest of the progression event subsequent to that used for the primary variable PFS or death. The date of second progression will be recorded by the Investigator and defined according to local standard clinical practice and may involve any of; objective radiological, CA-125 or symptomatic progression or death. Second progression status will be reviewed every 12 weeks following the progression event used for the primary variable PFS (the first progression) and status recorded. Patients alive and for whom a second disease progression has not been observed should be censored at the last time known to be alive and without a second disease progression, i.e. censored at the latest of the PFS or PFS2 assessment date if the patient has not had a second progression or death. If, however the patient progresses for the second time or dies after two or more missed visits, the patient will be censored at the time of the latest evaluable investigator - recorded assessment (see Section 3.2.1 for details).

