11.1.1 Progression Free Survival (PFS)

PFS is defined as the time from randomisation until the date of objective radiological disease progression according to RECIST or death (by any cause in the absence of progression) regardless of whether the patient withdraws from randomised study treatment or receives another anti-cancer therapy prior to progression. Patients who have not progressed or died at the time of analysis will be censored at the time of the latest date of assessment from their last evaluable RECIST assessment. However, if the patient progresses or dies after two or more missed visits, the patient will be censored at the time of the latest evaluable RECIST assessment. If the patient has no evaluable visits or does not have a baseline assessment they will be censored at day 1 unless they die within two visits of baseline. (25 weeks allowing for visit window).

The PFS time will always be derived based on scan/assessment dates not visit dates.

RECIST assessments/scans contributing towards a particular visit may be performed on different dates. The following rules will be applied:

- (a) Date of progression will be determined based on the **earliest** of the RECIST assessment/scan dates of the component that triggered the progression

- (b) When censoring a patient for PFS the patient will be censored at the **latest** of the RECIST assessment/scan dates contributing to a particular overall visit assessment

Overall visit assessments will be determined for each assessment (scheduled or unscheduled) and will contribute to the derivation of PFS.

Objective progression is defined as at least a 20% increase in the sum of the diameters of the target lesions (compared to previous minimum sum) or an overall non-target lesion assessment of progression or a new lesion. For patients with no evidence of disease at baseline, following a clinical complete response to chemotherapy, progression is defined by the detection of new lesions on follow-up radiological assessments.

The primary analysis will be based on the programmatically derived PFS based on investigator-recorded assessment of the radiological scans. A sensitivity analysis based on the independent central review (ICR) of the radiological scans will be carried out. A charter for the ICR will be developed in advance of the start of the study.

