11.1.2.2 Time to earliest progression by RECIST 1.1 or CA-125 or death

Progression or recurrence based on serum CA-125 levels will be defined on the basis of a progressive serial elevation of serum CA-125, according to the following modified GCIG criteria (note GCIG criteria is not validated for this trial population):

- Patients with elevated CA-125 pre-treatment (i.e. greater than the upper limit of normal (ULN)):-
 - (a) If CA-125 does not fall to within the normal range whilst on treatment then there must be evidence of CA-125 greater than, or equal to, 2 times the nadir value in the 28 day period before day 1 on 2 occasions at least 1 week apart.
 - (b) Where CA-125 does fall to within the normal range whilst on study treatment (and the patient has not already progressed by way of (a) above) then there must be evidence of CA-125 greater than, or equal to, 2 times the ULN on 2 occasions at least 1 week apart.

- Patients with CA-125 in the normal range pre-treatment must show evidence of CA-125 greater than, or equal to, 2 times the ULN on 2 occasions at least 1 week apart. CA-125 progression will be assigned the date of the first measurement that meets the criteria as noted.

Time to progression by RECIST or CA-125 progression or death is defined as the time from randomisation to the earlier date of RECIST or CA-125 progression or death by any cause. Patients without a CA-125 progression or a RECIST progression who are still alive at the time of analysis will be censored at their last evaluable RECIST assessment or their last available CA-125 measurement, whichever is the most recent at the time of the analysis. If a patient progresses or dies after two or more missed RECIST and CA-125 assessments, then the patient will be censored at the time of their last evaluable assessment. If only one assessment is missing during this period, no censoring is required.

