11.1.2.3 Time from randomisation to second progression (PFS2)

Time from randomisation to second progression is defined as the time from the date of randomisation to the earliest of the progression event subsequent to that used for the primary variable PFS or death. The date of second progression will be recorded by the investigator and defined according to local standard clinical practice and may involve any of; objective radiological, CA-125 or symptomatic progression or death. Second progression status will be reviewed every 12 weeks following the progression event used for the primary variable PFS (the first progression) and status recorded. Patients alive and for whom a second disease progression has not been observed should be censored at the last time known to be alive and without a second disease progression, i.e. censored at the latest of the PFS or PFS2 assessment date if the patient has not had a second progression or death).

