12.2.3 Analysis of secondary endpoints

12.2.3.1 Analysis of PFS2 endpoint

An initial PFS2 analysis will be performed at the same time as the primary analysis of PFS and will use the same methodology and model. A further analysis of PFS2 will be performed when the OS data are approximately 60% mature.

As a sensitivity, the analysis of PFS2 will be repeated in those patients whose gBRCAm status is confirmed by the central Myriad test. A KM plot of PFS2 in this subset of patients will be presented by treatment group.

The sensitivity analysis outlined for 12.2.2.1 will not be repeated for PFS2 with the exception of a Kaplan-Meier plot of the time to censoring where the censoring indicator of the primary PFS2 is reversed.

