Attrition bias will be assessed by repeating the primary PFS analysis except that the actual PFS event times, rather than the censored times, of subjects who progressed or died in the absence of progression immediately following two, or more, non-evaluable tumour assessments will be included. In addition, subjects who take subsequent therapy prior to their last evaluable RECIST assessments or progression or death will be censored at their last evaluable assessment prior to taking the subsequent therapy. Additionally a KM plot of the time to censoring where the censoring indicator of the primary PFS analysis is reversed (what was originally a censored event in the primary PFS analysis becomes an actual event and what originally was a PFS event becomes a censored event) will be presented.

(c) Ascertainment bias

A stratified log-rank test will be repeated using BICR RECIST data to programmatically derive PFS. The HR and 95% CI will be presented.

The type of event (RECIST or death) will also be provided.

If there is an important discrepancy between the primary analysis using investigator assessments and this sensitivity analysis using BICR assessments, then the proportion of subjects with site but no central confirmation of progression will be summarised. This scenario is possible as at the time of the primary analysis data cut off all scans will be sent for central review assessment regardless of whether or not a patient has been assessed as having progressed by the site. The approach of imputing an event at the next visit in the BICR assessed analysis may help inform the most likely HR value, but only if an important discrepancy exists.

Disagreements between investigator and BICR assessment of RECIST progression will be presented for each treatment group. The summary will include the early discrepancy rate which is the frequency of BICR progressions declared before the investigator review progressions (≥2 weeks earlier and including progressions declared by BICR but not investigator) as a proportion of all BICR progressions, and the late discrepancy rate which is the frequency of BICR progressions declared after the investigator review (≥2 weeks later and including progressions declared by investigator but not BICR as a proportion of all discrepancies (including early and late discrepancies) (Amit et al 2011).

(d) Deviation bias (if meaningful to do)

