6 CHANGES OF ANALYSIS FROM PROTOCOL

All efficacy and HRQoL will be analysed using FAS.

Section 3.2.1 Progression free survival

Added clarification that according to the RECIST 1.1 guidelines an overall visit response of PD also requires an absolute increase of > 5 mm in the sum of the diameters of the target lesions.

Section 3.2.7 Time to earliest progression by RECIST or CA-125 or death Derivations will be relative to randomization (CSP states start of study treatment). Also, censoring will use the earliest of the last evaluable RECIST assessment or the last available CA-125 measurement (CSP states most recent).

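### The SAP censors second progressions and deaths after two missed visits that the protocol counts as PFS2 events; the change is undeclared and no planned PFS2 analysis restores them

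*SAP*

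**What the plan says.** Protocol 11.1.2.3 takes as the PFS2 event the earlier of second progression (investigator-recorded, by local practice) or death. Its only censoring rule is for patients with neither: "Patients alive and for whom a second disease progression has not been observed should be censored at the last time known to be alive" and free of second progression. It has no missed-visit rule.

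The protocol does write such a rule for two other endpoints. For PFS (11.1.1): "if the patient progresses or dies after two or more missed visits, the patient will be censored". For RECIST or CA-125 progression (11.1.2.2): "If a patient progresses or dies after two or more missed RECIST and CA-125 assessments, then the patient will be censored".

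SAP 3.2.2 carries over the protocol's PFS2 text and adds: "If, however the patient progresses for the second time or dies after two or more missed visits, the patient will be censored". Censoring is at the latest evaluable investigator-recorded assessment, and the reader is sent to SAP 3.2.1 for details. There, two missed visits means a gap of more than 26, 38 or 50 weeks, depending on the date of the last evaluable assessment.

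SAP Section 6 declares a censoring change for RECIST/CA-125 progression ("censoring will use the earliest of the last evaluable RECIST assessment or the last available CA-125 measurement (CSP states most recent") but has no PFS2 entry.

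The attrition-bias analysis in SAP 4.2.2 uses the "actual PFS event times, rather than the censored times", for PFS. For PFS2, protocol 12.2.3.1 states: "The sensitivity analysis outlined for 12.2.2.1 will not be repeated for PFS2", apart from a reversed-censoring Kaplan-Meier plot. SAP 4.2.3 says the same.

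**The concern.** The same patient can be an event under one document and censored under the other, on an endpoint inside the multiple testing procedure. OS is tested only if PFS2 is significant (protocol 12.2.1, SAP 4.2.1), so the event set behind the PFS2 claim should not depend on which document is read.

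There is a concrete route by which known deaths drop out. SAP 4.2.14 has sites establish the status of withdrawn and lost patients at the PFS analysis, when the PFS2 interim is done, and at each planned OS analysis. SAP 3.2.3 allows death registries as a source. These patients are no longer attending, so their deaths can easily follow two missed visits. As an illustration, take a last evaluable assessment at week 60 and a traced death at week 96. The gap is 36 weeks, which exceeds 26. The death counts in OS and in protocol-defined PFS2, but under the SAP the patient is censored at week 60.

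Timing adds to the problem. SAP Section 5 shows that the PFS analysis preceded this SAP version, and the available text of neither document says which rule the PFS2 interim used. Protocol 12.2.1 and SAP 4.2.1 make the confirmatory retest conditional on a non-significant interim. If the interim was significant, the open question is which definition supports that claim.

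**Working it through.** **The definitions side by side**

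| Patient | Protocol 11.1.2.3 | SAP 3.2.2 |
|---|---|---|
| Second progression or death, fewer than two missed visits before it | event | event |
| Second progression or death after two or more missed visits | event | censored at last evaluable assessment |
| Alive, no second progression | censored | censored |

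Only the middle row differs. Protocol 12.2.3.1 says PFS2 is analysed with the methodology and model used for PFS, but that does not import the PFS missed-visit rule. Protocol 12.2.3.2 and 12.2.3.3 say the same of OS, TFST, TSST and TDT, none of which has such a rule in its definition. The phrase covers the test and model, not the derivation of events.

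**Planned PFS2 analyses (SAP Table 7 and 4.2.3)**

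- Stratified log-rank test: uses the SAP rule.
- Repeats in the Myriad-confirmed germline and Foundation Medicine-confirmed tumour subsets: no alternative censoring stated.
- Wei-Lin-Weissfeld marginal model: not described as restoring the events.
- Reversed-censoring Kaplan-Meier plot and by-arm summary of time from second progression to previous assessment: descriptive, no treatment effect.

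None estimates the PFS2 effect with these events counted.

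**The plan's own thresholds reproduced.** Inputs from protocol 12.2.1: 180 events at 1-sided 0.0125 (HR ≤ 0.70), and 300 events at 1-sided 0.018 (HR ≤ 0.77), with 2:1 allocation. Critical HR = exp(−z/√(d × 2/9)).

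- Interim: exp(−2.2414/√40) = 0.7016, stated as 0.70.
- Final: exp(−2.0969/√66.67) = 0.7735, stated as 0.77.
- Final alpha, with interim alpha 0.0125 at information fraction 180/300 = 0.6 and a total of 0.025: 0.0180, stated as about 1.8%.

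**Effect of losing events, with the observed effect unchanged.** Ten fewer events give 0.6944 at d = 170 and 0.7701 at d = 290, reductions of about 0.007 and 0.003. The documents give no rate of affected events, so the loss is an assumption:

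| Assumed loss | Interim events | Critical HR | Final events | Critical HR |
|---|---|---|---|---|
| 0% | 180 | 0.702 | 300 | 0.774 |
| 5% | 171 | 0.695 | 285 | 0.768 |
| 10% | 162 | 0.688 | 270 | 0.763 |
| 15% | 153 | 0.681 | 255 | 0.757 |

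If the loss is unrelated to arm, z shrinks by √(1 − f), where f is the fraction lost. At observed HR 0.69, 0.65 and 0.60, z = |ln HR| × √40 = 2.347, 2.725 and 3.231. Falling to 2.2414 needs f = 1 − (2.2414/z)², or about 16, 58 and 93 of the 180 events.

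**Assumed extreme: every removed event is on placebo.** The log-rank numerator is about |ln HR| × 40 = 14.84, 17.23 and 20.43 at those three HRs. The critical value is 2.2414 × √40 = 14.18. Removing one placebo event lowers the numerator by about 2/3, because the observed count falls by 1 and the expected count by about 1/3. Events needed:

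- HR 0.69: 0.667/0.667 = 1.0
- HR 0.65: 3.06/0.667 = 4.6
- HR 0.60: 6.26/0.667 = 9.4

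A simulation agrees, with median removals (10th–90th percentile) of 1 (1–2), 5 (4–6) and 10 (9–11). It used 391 patients split 261/130, 18-month uniform entry, exponential times, an assumed placebo PFS2 median of 42 months, a cut at 180 events, and removed events censored 7.5 months earlier. The median, the shift and uniform entry are assumptions, not plan figures. Removal on olaparib would act in the opposite direction.

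**The case against.** The missed-visit rule is already the protocol's convention for PFS and for RECIST/CA-125 progression, and it avoids counting events of uncertain timing. Extending it to PFS2 is defensible as a choice. That stands. It does not excuse leaving the change undeclared when Section 6 declares a comparable change for a supportive endpoint.

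The SAP is not blind to uneven follow-up: besides the PFS2 summaries listed above, SAP 4.2.2 tabulates missed RECIST assessments by arm. These could reveal an imbalance, but none gives a PFS2 hazard ratio with the events counted. OS and TSST do count the deaths, but they are different endpoints, and TSST is outside the multiple testing procedure.

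The size is not established, and the all-placebo case is a worst case; at HR 0.69 the result already sits next to the boundary. That is right, and the arm-neutral figures are the proper counterweight.

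The interim rule may be stated in material not available here, since part of protocol 12.2.5 is redacted. That limits the point about the interim, but the contradiction does not depend on it.

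Protocol 12.2.3.1 and the synopsis also plan a further PFS2 analysis at about 60% OS maturity without the condition that SAP 4.2.3 attaches. The fix has to work in either case.

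Finally, the 38- and 50-week windows follow the RECIST scan schedule although PFS2 is reviewed every 12 weeks. They censor fewer late events than a 12-weekly window would. This is a schedule mismatch to note, not a contradiction.

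**Conclusion.** The concern holds. The documents give different PFS2 event sets, SAP Section 6 does not declare the difference, and no planned PFS2 analysis estimates the effect with the censored events restored. This rests on the text alone and is firm. The number of affected events, the direction of any hazard ratio shift and any change in the PFS2 decision cannot be determined from the documents. Loss of events by itself is a minor matter; the risk lies in an imbalance between arms, which the plan does not test for PFS2. The point should be fixed because PFS2 is a confirmatory endpoint that gates OS.

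**What to change.** 1. Use one PFS2 censoring rule in both documents. Take the protocol definition unless the SAP rule was used at the PFS2 interim. In that case keep the SAP rule unchanged, windows included, declare it in SAP Section 6 and align protocol 11.1.2.3.
2. State in SAP 4.2.3 which rule the interim used.
3. Add a PFS2 sensitivity analysis under the other definition. If the SAP rule is the main one, this counts all second progressions and deaths at their actual dates. Prespecify it for any later PFS2 analysis; if none is planned, run it on the interim data and label it post hoc. Take over only the restored-event part of the PFS attrition-bias analysis. Leave out its other part, under which patients "will be censored at their last evaluable assessment prior to taking the subsequent therapy", because therapy between first and second progression is expected.
4. Note the window mismatch. If a 12-weekly window is of interest, examine it only as a sensitivity analysis, not as a post-interim change to the main rule.

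The cost is SAP wording, one line in Section 6 (with the matching protocol wording if the SAP rule is kept) and one extra PFS2 run. The downside is that the all-events version counts some events of uncertain timing, such as a registry death with no observed second progression.

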3.2.3 Overall survival (OS)

Overall survival (OS) is defined as the time from the date of randomisation until death due to any cause. Any patient not known to have died at the time of analysis will be censored based on the last recorded date on which the patient was known to be alive (SUR_DAT, recorded within the SURVIVE module of the eCRF).

Note: Survival calls will be made in the week following the date of DCO for the analysis, and if patients are confirmed to be alive or if the death date is post - DCO date these patients will be censored at the date of DCO. Death dates may be found by checking publicly available death registries.

